The Phase III clinical program of the dapivirine vaginal ring, containing 25 mg of dapivirine (Ring-004), consists of the MTN-020 and IPM 027 clinical trials. These trials are conducted in South Africa, Uganda, Zimbabwe and Malawi, to assess the safety and efficacy of the Dapivirine Vaginal Ring-004 in preventing the acquisition of HIV-1 infection through male to female transmission in healthy, HIV-negative women.

IPM 027 is a double-blind, multicentre, placebo-controlled trial that has been designed to assess the safety and efficacy of the Dapivirine Vaginal Ring-004, inserted once every 4 weeks over a period of 24 months, in healthy, sexually active HIV-negative women, 18 to 45 years of age, when compared to a placebo vaginal ring. It is conducted at 7 research centres, six in South Africa and one in Uganda. A total of 1959 eligible women were randomized in a 2:1 ratio to receive either the dapivirine vaginal ring or placebo vaginal ring. This trial was initiated in March 2012 and is expected to complete in 2016/2017.

MTN-020 has been designed to assess the safety and effectiveness of the Dapivirine Vaginal Ring-004, inserted once every 4 weeks, in healthy, sexually active, HIV-negative women, 18 to 45 years of age, when compared to a placebo vaginal ring. It is conducted in Malawi, South Africa, Uganda and Zimbabwe. A total of 2629 women were

randomized. Each participant will use the investigational product until 120 events (HIV-1 seroconversions) are observed in the trial. All participants are anticipated to use the investigational product for a minimum of 12 months. The trial was initiated in August 2012 and clinical conduct completed in June 2015.

1.4.3. *Adherence to and Acceptability of the Dapivirine Vaginal Ring*

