5.14. Vaginal Ring Insertion and Ring Removal

At the Enrolment and Trial Visits, participants will insert the vaginal rings under research centre supervision. The participant will be instructed to thoroughly wash her hands, relax, and get into a comfortable position either standing with one foot on a chair, lying on her back with her knees up, or squatting. After opening the folds of skin around the vagina, she will gently squeeze the ring into an oval shape and push it upwards and backwards towards the back as far as it will go, thereby depositing the ring in the vagina. She will then be instructed to thoroughly wash her hands again. At all research centre visits during which a pelvic examination is performed, the participant will remove the ring prior to the examination.

If the participant requests help with either removal or insertion of the vaginal ring, or after she has made several attempts to remove/insert the ring without success, trained trial staff may give assistance. Re-education of the participant on ring removal/re-insertion will be given. This will be noted in the source documents and applicable CRFs. Additional instructions about ring use will be provided in the SOM.

All rings that are removed will be inspected visually, and an assessment will be made by the principal investigator or designee as to whether the ring appears to have been used or not, together with a reason for the assessment. The rings should then be rinsed in running water, patted dry, placed in a ring return bag, and stored between 15°C and 30°C until shipment to the analytical laboratory for testing of residual dapivirine amounts.

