8.3. Sample Size and Power Calculations

This trial will be conducted in healthy, HIV-negative women who have participated in the IPM 027 trial. No formal sample size or power calculations have thus been performed.

It is expected that approximately 70% of the participants enrolled in IPM 027 will participate in this trial. Therefore, a total sample size of approximately 1400 HIV-negative women is anticipated.

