2.3 Exploratory Objectives

The exploratory trial objectives are:

- To assess the feasibility of 3-monthly follow-up visits, as a possible schedule for post-licensure vaginal ring clinical follow-up.
- To explore the correlation between drug concentrations and results from the visual inspection of the returned vaginal rings by research staff between the monthly and 3-monthly research centre follow-up schedules.
- To determine the proportion of participants electing to undergo HIV rapid tests at the research centres between scheduled 3-monthly visits.
- To characterize the IPM 027 participants who decline enrollment into IPM 032 (Decliner Population) [***Not implemented.***]
- To explore self-reported acceptability of and adherence to the 25 mg Dapivirine Vaginal Ring-004.

Note: Objectives indicated as “Not implemented” above, are not addressed in this analysis plan.

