In instances where the date of IP initiation, *i.e.* the start date of ring use, is missing or unknown, the missing date will be imputed with the date of the enrollment visit.

In accordance with the protocol, each scheduled visit has a window period of \pm 7 days. If the participant does not return to the research centre for a scheduled visit prior to the start of the trial window of the next visit, the visit will be considered missed. If a participant presents for a visit outside the window for a scheduled trial visit, but prior to the start of the window for the next visit, it will be treated as a late visit. Missed visits and late visits will be documented as protocol deviations (refer to Section 7.2). Data recorded at late visits will be analysed as pertaining to the scheduled visit. Unscheduled visits may be performed at any time during the trial. If an unscheduled visit takes place within any given window period and any repeat observations are made within the given window period, the repeat values will be captured as pertaining to the unscheduled visit. Data from scheduled and unscheduled visits will be shown in the participant listings, and listings will be appropriately labelled when data arise from unscheduled visits. Data from scheduled visits will be presented in the summary tables.

Visit Schedule A will consist of participants who attend Trial Month Visits 1, 4, 7, 10, 13, and 16/Exit; Visit Schedule B will consist of participants who attend Trial Month Visits 1, 2, 5, 8, 11, 14, and 17/Exit; and Visit Schedule C will consist of participants who attend Trial Month Visits 1, 2, 3, 6, 9, 12, and 15/Exit.

Tables, figures, and listings of trial results will accompany the text of the CSR. Listings of all clinical data recorded in the CRFs will be provided, except for those CRFs which are used for administrative purposes, such as the Participant Encounter Form (PEN) and the End of Trial Inventory (ETI). Listings will be sorted by research centre and participant identification number (PID), and key variables such as visit date and/or trial visit number will be presented in each listing.

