9.2 Primary Endpoint 2 – Adherence

Dapivirine residual levels in used rings will be determined for all participants receiving IP, as a measure of adherence to ring use. The data will be listed, summarised and presented graphically, as described below.

Dapivirine Residual Levels in Used Rings

All used vaginal rings that are returned to the research centres at each trial visit are collected and shipped at regular, pre-defined intervals to an analytical laboratory,

where the rings are analysed to determine the residual amounts of dapivirine in the rings.

For this trial, a reported ring residual level of > 23.5 mg dapivirine will be used as an indication of non-adherence to ring use over the 30-day period (± 7 days) that a woman was to keep the ring *in situ*. Based on the data from the Phase III program, the cut-off value of > 23.5 mg for dapivirine ring residual levels was shown to be a good measure of non-adherence to ring use, indicating no or very little ring use.

The following summaries and graphical presentations will be produced for these data:

- A summary of ring residual levels at each trial visit and at the time of seroconversion, the time of first HIV-1 RNA positive as well as the time of last HIV-1 RNA negative will be presented with standard descriptive statistics – presented overall, by IPM 027 treatment arm, and by research centre. Corresponding box plots will be prepared.
- A descriptive summary of the ring residual levels by trial visit and by category of residual amount (< 20 mg, $20 – 21$ mg, $> 21 – 22$ mg, $> 22 – 23.5$ mg, and > 23.5 mg). This summary will be prepared overall, by IPM 027 treatment arm and by research centre, with corresponding bar charts.
- A summary relating the ring residual levels to time intervals (in days) between consecutive ring replacements (< 23 days, $23 – 37$ days, $> 37 – 84$ days, and > 84 days). Corresponding box plots will be prepared.

Note: All summaries and graphical presentations will be produced for both uncorrected dapivirine ring residual levels (as reported by the analytical laboratory) and residual levels corrected for manufacturing and assay variability, unless otherwise specified.

The aforementioned graphical presentations will be repeated for the ring residuals from the IPM 027 and IPM 032 trials, and will be based only on the participants from IPM 027 who enrolled in IPM 032. However, only the uncorrected ring residual levels will be used.

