At all trial visits and the last product use visit, the RL CRF will be completed, indicating the rings dispensed at each trial visit (items 1 and 2) and the used / unused rings returned at each trial visit (items 7 and 8).

Statistical methods

The analysis of feasibility of the 3-monthly clinical follow-up schedule will be primarily descriptive in nature, and will include absolute and relative frequencies for each trial visit for Participant Questionnaire items listed above, overall and by Visit Schedule (A, B or C). In particular, the number and percentage of women opting not to receive two additional rings at the 3-monthly clinical follow-up schedule will be reported.

The proportion of returned rings (used and unused) during the 3-monthly clinical follow-up schedule will also be reported. This will be calculated as the number of used/unused rings returned divided by the number of rings dispensed.

9.4.2 Exploratory Endpoint 2: Correlation between dapivirine residual amounts in returned used vaginal rings and/or drug concentrations, and results from visual inspection of returned vaginal rings

Consistent with exploratory objective 2, exploratory endpoint 2 is the dapivirine ring residual levels in returned used vaginal rings and/or dapivirine concentrations in plasma and/or vaginal fluid (not assayed) in correlation with results from the visual inspection of the returned used vaginal rings by research staff.

Assessments

At all trial visits and the last product use visit, the RL CRF will be completed, indicating the rings dispensed at each trial visit (items 1 and 2) and the appearance of used/unused rings returned at each trial visit (items 7, 8 and 9).

Residual levels of dapivirine in used rings will be determined for all participants receiving IP at each trial visit.

Statistical methods

The correlation between the amount of corrected residual dapivirine in the used vaginal rings and the corresponding results from the visual inspection of the returned used vaginal rings, will be explored descriptively by producing summary statistics and

a corresponding scatter plot of the dapivirine levels for each category of appearance and colour of the returned ring.

9.4.3 Exploratory Endpoint 3: Proportion of participants opting for HIV rapid tests at the research centre between scheduled 3-monthly visits

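### The residual-level and visual-inspection tables are not split by schedule or ring position, so the monthly versus 3-monthly comparison in exploratory objective 2 is not made

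*SAP*

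**What the plan says.** SAP 2.3, objective 2, sets out to explore how drug levels correlate with the visual inspection of returned rings "by research staff between the monthly and 3-monthly research centre follow-up schedules". Plasma and vaginal fluid were not assayed (SAP 2.4), so the residual amount in the ring is the measure that remains. For this objective SAP 9.4.2 plans summary statistics and "a corresponding scatter plot of the dapivirine levels for each category of appearance and colour of the returned ring"; Table 14.6.2 adds the month in which the ring was used.

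For the primary adherence endpoint, SAP 9.2 summarises residual levels by trial visit and, for the categories, states: "This summary will be prepared overall, by IPM 027 treatment arm and by research centre, with corresponding bar charts". The shells for Tables 14.3.5.1 and 14.3.5.2 have rows by month of use. The adherence subgroups in SAP 6.5 are age, marital status, main partner and genital symptoms or STIs.

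Rings are delivered in two ways. Protocol 5.14 says: "At the Enrolment and Trial Visits, participants will insert the vaginal rings under research centre supervision". Once a woman is on 3-monthly visits, two further rings are normally taken away and inserted at home one and two months later (Protocol synopsis, Trial Visits; Protocol 5.13). SAP 6.6 defines three visit maps, the first being: "Visit Schedule A will consist of participants who attend Trial Month Visits 1, 4, 7, 10, 13, and 16/Exit".

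The SAP does use Schedules A, B and C elsewhere: for disposition (7.1), HIV-1 incidence (9.3.1), resistance (9.3.2) and the feasibility items (9.4.1).

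**The concern.** A stated objective has no analysis that answers it. Nothing in SAP 9.4.2 or Table 14.6.2 distinguishes a monthly-phase ring from a 3-monthly-phase ring, and the primary residual-level tables do not either.

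A reader of the finished tables would probably use the month rows as a stand-in, since early months are mostly monthly-phase and later months are all 3-monthly. That fails because the make-up of the rows changes over the first few months. If take-home rings were used less well, the change in make-up would look like adherence falling with time on the trial. The trial's objective measure of ring use would then be silent on whether the dispensing pattern mattered.

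**Working it through.** **Planning figure.** The documents give no figure for this point; Protocol 8.3 states that "No formal sample size or power calculations have thus been performed". The one planning number is the expected enrolment: 0.70 × 1959 = 1371, against approximately 1400. It reproduces, but has no bearing here.

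**Step 1: map each ring to its delivery.** Inputs are the visit months in SAP 6.6 and the rule that the first ring after each visit is inserted at the visit and the next two at home. Months are months of insertion, enrolment = 0. Month 13 (A), 14 (B) and 12 (C) are taken as last product-use visits; rows 2 to 11 do not depend on this.

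| Inserted at month | A | B | C | Take-home share, equal thirds |
|---|---|---|---|---|
| 0, 1 | visit | visit | visit | 0 |
| 2 | home | visit | visit | 1/3 |
| 3 | home | home | visit | 2/3 |
| 4, 7, 10 | visit | home | home | 2/3 |
| 5, 8, 11 | home | visit | home | 2/3 |
| 6, 9 | home | home | visit | 2/3 |
| 12 | home | home | none | 1 |
| 13 | none | home | none | 1 |

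Rows 0 and 1 are all visit-inserted, rows 2 to 11 are mixed, and rows 12 and 13 are take-home only.

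**Step 2: map each ring to its phase.** The enrolment ring is monthly-phase for everyone. At month 1, A has started a 3-monthly cycle; at month 2, so has B; from month 3, everyone has, apart from women who choose to collect rings at interim visits. The two phases coexist only for rings inserted at months 1 and 2.

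**Step 3: what the pooled rows would show.** Assumed, not in the documents: a percentage *v* of visit-inserted and *w* of take-home rings exceed 23.5 mg, both constant over time. With take-home share *h*, each row reads *v* + (*w* − *v*) × *h*. Take *v* = 10% and equal thirds, and compare the first three months of use (inserted at 0 to 2) with months of use 10 to 12 (inserted at 9 to 11):

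| *w* | First three months | Months of use 10 to 12 |
|---|---|---|
| 10% | 10.0% | 10.0% |
| 15% | (10 + 10 + 11.7)/3 = 10.6% | 10 + 5 × 2/3 = 13.3% |
| 20% | (10 + 10 + 13.3)/3 = 11.1% | 10 + 10 × 2/3 = 16.7% |
| 30% | (10 + 10 + 16.7)/3 = 12.2% | 10 + 20 × 2/3 = 23.3% |

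At *w* = 20% with other mixes: 13.3% versus 16.7% (all A), 11.7% versus 16.7% (50/30/20), 10.0% versus 16.7% (all C).

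**Step 4: shape.** With equal thirds the pattern is an early rise in non-adherence and then a level stretch to month 11. If one schedule dominates it is a three-month sawtooth. Rows 12 and 13 would read *w*. If the effect instead belongs to the whole 3-monthly phase, with 20% against 10% and equal thirds, rows 0 to 3 read 10.0%, 13.3%, 16.7% and 20.0%, then stay flat.

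**The case against.** The strongest reply is that this is an exploratory objective with loose wording. The matching exploratory endpoint in Protocol 2.2 and SAP 2.4 does not mention the two schedules, and SAP 9.4.2 follows the endpoint. Protocol 8.4 leaves the models for the exploratory objectives to the SAP. That stands against calling the gap an undeclared change to a protocol-planned analysis, but SAP 2.3 keeps the comparison as an objective and no section carries it out.

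Table 14.3.5.3 relates residual levels to the replacement interval and so partly captures late home replacement. It does not separate the ring types, because rings of either type replaced on time fall in the same 23 to 37 day row. The per-ring listings and the allowance in SAP 1 for further exploratory analyses make a later split possible, but do not pre-specify one.

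Three stronger readings are tempting and not supported. First, a reader might infer that the plan promises a comparison of centre-inserted with home-inserted rings. It does not: objective 2 contrasts follow-up schedules, and the primary adherence objective and Protocol 8.4.2 promise neither contrast. Second, a reader might infer that residual levels are the core of the feasibility question. The documents assess feasibility by questionnaire, by the number declining extra rings and by the proportion of rings returned, and SAP 9.4.1 and Table 14.6.1 plan these by schedule. Third, a reader might infer that comparing rings within one 3-monthly interval isolates home use. It avoids selection by schedule, but the visit-inserted ring normally comes first, so place cannot be separated from ring order or time since counselling.

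**Conclusion.** The point holds in limited form. The schedule comparison in exploratory objective 2 is not made, and the primary residual-level tables have no split that would supply it. The month rows cannot stand in for one: their make-up shifts over the first months, and rows 2 to 11 mix ring types.

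The size is conditional. Under the assumed rates and equal thirds, the spurious rise between the first three months and months of use 10 to 12 runs from 2.8 points (13.33 − 10.56) to 11.1 points (23.33 − 12.22), and is zero if the ring types are used equally well. A reader might infer that any fall in the reported adherence will be an artefact; nothing in the documents shows that. Supervision covers insertion, whereas the 23.5 mg cut-off reflects wear over about 30 days, so a large difference is not self-evident.

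The affected tables are descriptive and the objective is exploratory. The change is still worth making, because the omission is specific and the data already exist.

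**What to change.** Derive a ring-level factor from the ring log fields shown in Listing 16.2.5.4 (visit dispensed, dispensing date, insertion date), with four levels:

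- monthly-phase ring;
- first ring of a 3-monthly cycle;
- second or third ring of a 3-monthly cycle;
- ring collected at an interim visit.

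Repeat Tables 14.3.5.1, 14.3.5.2 and 14.6.2 by this factor. Visit Schedule alone, pooled over months, would not separate the ring positions.

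Label the results descriptive and give the reasons: the investigator chooses the schedule; monthly-phase and 3-monthly-phase rings overlap only in the first months; place of insertion is inferred from dates and dispensing visit; and a within-interval contrast cannot separate home use from ring order. Since Protocol 6.5 lets a spare ring replace a lost or expelled one, use the listed replacement flag to identify such rings. SAP 1 notes that the ring log form was revised during the trial, so check that the fields exist in both versions.

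The cost is SAP wording and three table repeats, with no new data collection. If the sponsor does not want the comparison, SAP 11 should state that the schedule element of objective 2 is dropped.

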9.3 Secondary Endpoints

9.3.1 Secondary Endpoint 1: HIV-1 seroconversion rate per 100 person-years of product use

Consistent with secondary objective 1, secondary endpoint 1 is the HIV-1 seroconversion rate per 100 person-years of product use at the end of the vaginal ring use period.

Assessments

Trial participants will be tested for HIV-1 infection at all trial visits until the last product use visit, and at the exit visit, 1-2 months after ring discontinuation. HIV-1 seroconversion will be determined per the HIV testing algorithm presented in the IPM 032 protocol (Appendix B) and assessed by the Principal investigator or dedicated sub-investigator at the research centre and the IPM clinical physician to confirm HIV-1 seroconversion and estimated point of infection⁵. The HSMC was established to act in advisory capacity as IPM 032 secondary endpoints did not require independent evaluation of HIV-1 seroconversions and/or HIV-1 trial endpoints. The HSMC was consulted on an ad hoc basis, e.g. regarding inconclusive or atypical HIV test results. The point of HIV-1 infection was estimated by performing reverse sequential HIV Ribonucleic Acid (RNA) Polymerase Chain Reaction (PCR) testing (on stored samples collected at each visit) until a negative test result is achieved.

Statistical methods

Participants who are not diagnosed with HIV-1 using seroconversion testing at the end of the trial participation period will be censored at the last HIV-1 test date, at or prior to the last product use visit.

If HIV-1 is detected at the Exit visit, HIV-1 RNA PCR testing will be performed on stored samples in reverse sequential order to estimate the time point of HIV-1 infection.

- If HIV-1 infection is detected at or prior to the last product use visit, the participant will be included in the analysis as an HIV-1 seroconverter.
- If the time of infection is determined to be after completion of product use, the participant will be censored on the last HIV-1 test date at or prior to the last product use visit.

This analysis (Analysis 1) will be performed on the m-ITT population, as well as on the PP population.

Three additional analyses of HIV-1 seroconversion rate will be performed:

- Analysis 2: In instances where it cannot be ruled out that HIV-1 infection may have occurred during IP use due to atypical/inconclusive HIV RNA PCR test results or extended periods of non-product use, such participants will be considered as HIV-1 infected on product in this analysis.
- Analysis 3: All confirmed HIV-1 seroconverters determined to have been HIV-1 infected after enrollment will be considered as infected on product, even in instances where HIV-1 seroconversion and estimated point of infection was determined to be after the last product use visit.
- Analysis 4 (HIV-1 infection rate): Similar to Analysis 1, but based on time to first positive HIV-1 RNA.

All additional analyses will be performed on the m-ITT population.

For the number of participants included in the m-ITT analysis in IPM 032, matching placebo participants will be resampled with replacement from the IPM 027 trial, based on research center, age and STI prevalence at screening. These factors were selected because of their strong association with HIV incidence.

Age categories (18-24, and \geq 25 years) will be used to ensure that a sufficient number of participants are represented in each combination of categories of age, center and STI prevalence at screening (Yes/No). This resampling will be repeated 10 000 times; by ordering the 10 000 incidence rates and taking the 250th and 9750th value, a 95% confidence interval can be established. The placebo ring data of the complete double-blind period of IPM 027 will be used for this simulation.

The incidence of HIV-1 seroconversions, the incidence density rate of HIV-1 seroconversion (*i.e.* HIV-1 seroconversion rate per 100 person-years of product use at the end of the ring use period) as well as a 95% confidence interval for the HIV-1 seroconversion rate per 100 person-years (based on the normal approximation of the Poisson distribution) may be presented for the simulated placebo and treatment arm, overall and for each research centre. Similarly, the incidence of HIV-1 seroconversions, the incidence density rate and 95% CI will be presented by visit schedule (A, B or C) and overall. The 95% CI will be calculated using the formula below:

$$95\% \text{ confidence interval} = [(n/PY) \pm 1.96 \times (\sqrt{n/PY} / PY)] \times 100$$

where:

n = number of HIV-1 seroconversions

PY = total number of person-years of product use

Kaplan-Meier curves, of time to HIV-1 seroconversion will be presented, overall and by research centre using PROC LIFETEST in SAS®.

The time to event will be calculated as follows:

Time to event (days) = (Date of seroconversion/Censoring Date – Date of first ring use) + 1

Individual participant profiles for participants that seroconverted (listings and/or graphical presentations) may be produced, including potential prognostic factors (age, marital status, number of male partners, presence of STIs at baseline, number of sex acts, condom use during last round of vaginal sex, anal sex since last visit), occurrence of urogenital AEs, dapivirine ring residual levels over time, colour and appearance of returned rings, the estimated point of HIV-1 infection, and point of HIV-1 seroconversion.

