3.2. Trial Duration

Each participant will engage in the screening process for up to 45 days prior to enrolment and will use the Dapivirine Vaginal Ring-004 for a period of up to 12 months. IPM will have the option to extend this trial period. Accrual will take place over approximately 6 months and those participants who are enrolled more than 6 months after the onset of the study site's accrual period may have a shortened follow-up period.

Each participant will have an exit visit 1-2 months after ring discontinuation, to assess safety and identify HIV seroconversions after product discontinuation.

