Visit Schedule A = Participants attended trial month visit 1, 4, 7, 10, 13 and 16/Exit

Visit Schedule B = Participants attended trial month visit 1, 2, 5, 8, 11, 14 and 17/Exit

Visit Schedule C = Participants attended trial month visit 1, 2, 3, 6, 9, 12 and 15/Exit

Table 14.1.1.2
 Analysis Population Assignment
 Safety Population

	Statistic	Centre 01	Centre 02	...	Centre 08	All Centres
Safety population	N	XXX	XXX	...	XXX	XXX
m-ITT population	n (%) ^a	X (X.X)	X (X.X)	...	X (X.X)	X (X.X)
Virology population	n (%) ^a	X (X.X)	X (X.X)	...	X (X.X)	X (X.X)
PP population	n (%) ^a	X (X.X)	X (X.X)	...	X (X.X)	X (X.X)

m-ITT = Modified intent-to-treat; PP = Per-protocol

^a Percentages are calculated out of the participants in the safety population per centre

Centre 01: Madibeng Centre for Research (MCR); Centre 02: MatCH Research Unit (MRU); Centre 04: Qhakaza Mbokodo (QM);

Centre 06: MRC/UVRI & LSHTM Uganda Research Unit (MRC/UVRI); Centre 07: Desmond Tutu HIV Foundation (DTHF), Masiphumelele; Centre 08: Ndlovu Care Group (NCG)

Table 14.1.1.3
Protocol Deviations
Safety Population

Subgroup: All IPM 032 participants	Statistic	Centre 01 (N=XXX)	Centre 02 (N=XXX)	...	Centre 08 (N=XXX)	All Centres (N=XXX)
Participants with no reported protocol deviations	n (%) ^a	X (X.X)	X (X.X)	...	X (X.X)	X (X.X)
Participants with reported protocol deviations*	n (%) ^a	X (X.X)	X (X.X)	...	X (X.X)	X (X.X)
Minor deviations	n (%) ^b	X (X.X)	X (X.X)	...	X (X.X)	X (X.X)
Major deviations	n (%) ^b	X (X.X)	X (X.X)	...	X (X.X)	X (X.X)
No classification	n (%) ^b	X (X.X)	X (X.X)	...	X (X.X)	X (X.X)
Deviation criteria*						
Inappropriate enrollment (failed to meet eligibility criteria)	n (%) ^b	X (X.X)	X (X.X)	...	X (X.X)	X (X.X)
Missed visit	n (%) ^b	X (X.X)	X (X.X)	...	X (X.X)	X (X.X)
Visit completed outside of permissible window	n (%) ^b	X (X.X)	X (X.X)	...	X (X.X)	X (X.X)
Informed consent process deviations	n (%) ^b	X (X.X)	X (X.X)	...	X (X.X)	X (X.X)
Investigational product deviations	n (%) ^b	X (X.X)	X (X.X)	...	X (X.X)	X (X.X)
Safety reporting deviations	n (%) ^b	X (X.X)	X (X.X)	...	X (X.X)	X (X.X)
Failure to discontinue investigational product	n (%) ^b	X (X.X)	X (X.X)	...	X (X.X)	X (X.X)
Inappropriate treatment/management of medical conditions and follow-up of AEs	n (%) ^b	X (X.X)	X (X.X)	...	X (X.X)	X (X.X)
Mishandled laboratory samples	n (%) ^b	X (X.X)	X (X.X)	...	X (X.X)	X (X.X)
Missing or incorrectly timed trial procedures	n (%) ^b	X (X.X)	X (X.X)	...	X (X.X)	X (X.X)

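### The simulated IPM 027 placebo interval takes its width from the size of IPM 032, not from the number of placebo women, so its 95% label holds only if the two happen to match

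*SAP*

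**What the plan says.** SAP 9.3.1 (Secondary Endpoint 1, Statistical methods) sets up an external placebo reference for the HIV-1 seroconversion rate. On how many women to draw: "For the number of participants included in the m-ITT analysis in IPM 032, matching placebo participants will be resampled with replacement". Matching is on research centre, age in two categories, and STI at screening. On the interval: "by ordering the 10 000 incidence rates and taking the 250th and 9750th value, a 95% confidence interval can be established". On the source: "The placebo ring data of the complete double-blind period of IPM 027 will be used for this simulation". Nothing in SAP 9.3.1 or elsewhere rescales the interval to the number of placebo women who supplied the data.

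The size of that source follows from Protocol 1.4.2: "A total of 1959 eligible women were randomized in a 2:1 ratio to receive either the dapivirine vaginal ring or placebo vaginal ring". SAP 3.2 anticipated about 1400 women in IPM 032, from a roll-over of about 70% of IPM 027. Neither document gives the final m-ITT count or the number of placebo women available for matching.

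**The concern.** A bootstrap percentile interval reflects the uncertainty of an estimate when the resample is the same size as the sample it is drawn from. Here the two sizes are unrelated. Under this rule, enrolling more women in IPM 032 would narrow the placebo interval without adding one placebo observation.

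All IPM 032 participants receive the dapivirine ring, so this resampled group is the trial's only placebo benchmark. If N is well above the usable pool, the placebo rate looks better known than it is, and the IPM 032 rate looks more clearly separated from it. If N is below the pool, the distortion runs the other way.

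**Working it through.** **Inputs**
- Resample size m = N, the IPM 032 m-ITT count (SAP 9.3.1). Planning value about 1400 (SAP 3.2). Check: 0.70 × 1959 = 1371, within 3% of 1400.
- Placebo pool n: 1959 / 3 = 653 at most (Protocol 1.4.2).
- Centres: IPM 027 "It is conducted at 7 research centres, six in South Africa and one in Uganda"; the IPM 032 table shells in SAP Appendix 1 list six (01, 02, 04, 06, 07, 08).

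**The plan's own figure.** (9750 − 250) / 10 000 = 0.95. The percentile level is right; the question is what the 10 000 rates vary around.

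**Formula.** The standard error of the placebo rate is proportional to 1/√n. The spread of the resampled rates is proportional to 1/√m. Hence
- width ratio (planned / correct) = √(n/m)
- coverage = 2Φ(1.96 × √(n/m)) − 1

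**Planning figures.** √(653/1400) = 0.683; coverage = 2Φ(1.339) − 1 = 81.9%. With N = 1371: ratio 0.690, coverage 82.4%.

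**One centre unmatched.** Assume seven centres of equal size (not stated in the documents). The pool falls to 653 × 6/7 = 560, but so does the expected roll-over: 0.70 × 1959 × 6/7 = 1175. √(560/1175) = 0.69, coverage again about 82%. Losing a centre changes both numbers in proportion and leaves the ratio alone.

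**Sensitivity to the unknown N, pool 653**

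| N | Width ratio | Coverage |
|---|---|---|
| 1400 | 0.68 | 81.9% |
| 1000 | 0.81 | 88.7% |
| 900 | 0.85 | 90.5% |
| 700 | 0.97 | 94.2% |
| 653 | 1.00 | 95.0% |
| 450 | 1.20 | 98.2% |

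**Why it is the effective pool that counts.** Let stratum h have n_h placebo women, target share w_h and per-woman variance s_h². The planned draw takes w_h × N women from it, which gives variance Σ w_h s_h² / N. The true variance is Σ w_h² s_h² / n_h. They agree when N = Σ w_h s_h² / Σ (w_h² s_h² / n_h), which equals n if the IPM 032 mix matches the placebo mix and generally differs from n if it does not.

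**Simulation check** (assumed rates, up to 2 years per woman; illustrative only). Pool 653, N = 1400:
- Unstratified, planned rule: coverage 80.4% at 4 and 82.3% at 6 per 100 person-years.
- Stratified by centre, age and STI with a common mix, planned rule: 81.2%.
- Resample size set to the pool, unstratified: 94.4% and 95.1%.

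At N = 1400 the mean stratified width was 1.91 per 100 person-years for a pool of 653 and also for a pool of 560. The interval did not respond to the amount of placebo data.

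**The case against.** **A same-size comparator may be the aim.** The SAP speaks of a simulated placebo arm, and drawing N women makes it match IPM 032 in number as well as in mix. That is a coherent reason for m = N, but it does not support the label. A range for a new placebo group of size N must include the sampling error of the pool itself, and this one does not. Read as a prediction range, its coverage is 2Φ(1.96/√(1 + m/n)) − 1 = 73.1% at m = 1400, n = 653. Such a group would also differ from IPM 032 in planned follow-up: the IPM 027 ring was "inserted once every 4 weeks over a period of 24 months", whereas an IPM 032 participant "will use the Dapivirine Vaginal Ring-004 for a period of up to 12 months".

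**The figure of 1400 is only a planning value.** This stands. SAP 3.2 puts it in the past tense. A reader might infer that the reported interval will be too narrow by a third; the documents do not support that. With N near the usable pool the error is small, and with N below it the interval is too wide.

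**A lower figure, about 79%, is tempting.** A reader could pair a six-centre pool of 560 with N = 1400. Those inputs conflict: 1400 rests on about 70% of all seven centres' enrolees. Consistent inputs give about 82% with or without the seventh centre.

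**Weight.** Also granted: Protocol 8.4 calls this analysis descriptive, no test or margin uses the interval, and the shells for Analyses 1 to 4 (Tables 14.3.7.5 to 14.3.7.8) have no place for it. Their IPM 027 Placebo column appears to be IPM 032 women classed by former arm, since percentages are taken per IPM 027 treatment. But the resampling itself is planned without condition, and SAP 1 foresees use of the analyses in regulatory submissions or manuscripts.

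**Conclusion.** The interval is wrongly constructed as written. Its width is set by the IPM 032 m-ITT count, so it is a 95% confidence interval for the matched placebo rate only if that count happens to equal the effective placebo pool. At the planning assumption it covers about 82%, at about 0.68 of the proper width. This rests on a pool at its upper bound of 653, N of about 1400, and similar stratum mixes in the two trials. The mechanism is certain from the text; the size and direction of the error in the final analysis are not, because the actual N and usable pool are not given. It should be fixed, but nothing primary depends on it: the IPM 032 rate, its own interval, and the safety and adherence endpoints are untouched.

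**What to change.** In SAP 9.3.1, separate the matching from the resample size:
- Within each centre × age × STI stratum, resample with replacement the number of placebo women that stratum has in IPM 027.
- Weight the stratum results to the IPM 032 m-ITT mix, and take the 2.5th and 97.5th percentiles as the 95% confidence interval.
- State beforehand how sparse or empty strata are merged. With six centres there are 24 cells, about 23 women each on average if the pool is 560.
- Report the number of placebo women used.

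Setting the total resample size to the pool but drawing in IPM 032 proportions is not enough when the mixes differ. In one simulated example with an older IPM 032 mix (pool 560) that gave 91.8%. Resampling by stratum and weighting gave 94.0% in a separate example with unequal age mixes (pool 653, N = 900).

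If a range for a same-size simulated placebo group is what is wanted, do not call it a 95% confidence interval, and add the pool's own sampling error.

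Cost: some extra code, a merging rule and a few lines of SAP text. With a pool of 653, the placebo interval becomes 1/0.683 = 1.46 times as wide at N = 1400 and 1/0.852 = 1.17 times at N = 900. It becomes narrower if N is below the pool.
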